## Severe Cutaneous Reactions Including Hypersensitivity Reactions

Angioedema and severe cutaneous reactions including Stevens-Johnson syndrome (SJS), toxic epidermal necrolysis (TEN) and drug reaction with eosinophilia and systemic symptoms (DRESS) have been reported.

DRESS may present with a cutaneous reaction (such as rash or exfoliative dermatitis), eosinophilia, fever, and/or lymphadenopathy with systemic complications such as hepatitis, nephritis, pneumonitis, myocarditis, and/or pericarditis. Discontinue POMALYST for angioedema, skin exfoliation, bullae, or any other severe cutaneous reactions such as SJS, TEN or DRESS, and do not resume therapy

## Hematologic Toxicity

In trials 1 and 2 in patients who received pomalidomide + low-dose dex, neutropenia was the most frequently reported Grade 3/4 adverse reaction, followed by anemia and thrombocytopenia. Neutropenia of any grade was reported in 51% of patients in both trials. The rate of Grade 3/4 neutropenia was 46%. The rate of febrile neutropenia was 8%. Monitor patients for hematologic toxicities, especially neutropenia. Monitor complete blood counts weekly for the first 8 weeks and monthly thereafter. Patients may require dose interruption and/or modification

## Thrombocytopenia

Blood counts should be monitored regularly as outlined in the protocol with additional testing obtained according to standard clinical practice. Thrombocytopenia may be severe but has been manageable with platelet transfusions according to standard clinical practice. Pomalidomide administration should be modified as noted as per dose modification recommendations in the protocol when thrombocytopenia occurs (see Table 6-4). Therapy can be reinitiated at a reduced level upon recovery of platelet counts.

## Neutropenia

Blood counts should be monitored regularly as outlined in the protocol with additional testing obtained according to standard clinical practice. Neutropenia may be severe but has been manageable. Growth factor support is not required but may be considered according to standard clinical practice. Pomalidomide administration should be modified as noted as per

dose modification recommendations in the protocol when neutropenia occurs (see Table 6-4). Therapy can be reinitiated at a reduced level upon recovery of ANC.

#### Dizziness and Confusional State

In trials 1 and 2 in patients who received pomalidomide + low-dose dex, 14% of patients experienced dizziness and 7% of patients experienced a confusional state; 1% of patients experienced Grade 3 or 4 dizziness, and 3% of patients experienced Grade 3 or 4 confusional state. Instruct patients to avoid situations where dizziness or confusional state may be a problem and not to take other medications that may cause dizziness or confusional state without adequate medical advice.

#### Neuropathy

In trials 1 and 2 in patients who received pomalidomide + low-dose dex, 18% of patients experienced neuropathy, with approximately 12% of the patients experiencing peripheral neuropathy. Two percent of patients experienced Grade 3 neuropathy in trial 2. There were no cases of Grade 4 neuropathy adverse reactions reported in either trial.

#### Risk of Second Primary Malignancies

Cases of acute myelogenous leukemia have been reported in patients receiving pomalidomide as an investigational therapy outside of multiple myeloma.

#### Tumor Lysis Syndrome

Tumor lysis syndrome (TLS) may occur in patients treated with pomalidomide. Patients at risk for TLS are those with high tumor burden prior to treatment. These patients should be monitored closely and appropriate precautions taken.

## **6.8 Preparation, Reconstitution, and Dispensing**

Caution should be exercised when preparing daratumumab.

## **6.9 Packaging and Labeling**

### Daratumumab

The study drug daratumumab will be provided by Janssen Scientific Affairs, LLC. Packaging and labeling guidelines will be followed per manufacturer's instructions.

### Pomalidomide

Commercial pomalidomide is planned for use.

### Dexamethasone

The study drug dexamethasone will be commercially obtained and packaging and labeling guidelines will be followed per manufacturer's instructions.

## **6.10 Storage, Handling, and Accountability**

## Daratumumab

The final daratumumab SC product for oncology/hematology is daratumumab at a target concentration of 120 mg/mL co-formulated with rHuPH20 in a 25R vial at a nominal fill to deliver 15 mL. As a bridging strategy, administration of daratumumab by the SC route was after mixing the daratumumab IV drug product with rHuPH20 in polypropylene syringes.

Upon receipt at the investigative site, daratumumab vials should be stored in the original carton in a refrigerator at 2°C to 8°C and must not be utilized after the expiry date printed on the label. The product must be protected from light and must not be frozen. Since daratumumab does not contain preservatives, any unused portion remaining in the vial must be discarded.

## Dexamethasone

Dexamethasone will be handled and stored as per manufacturers package insert.

### **6.11 Termination of Treatment and/or Study Participation**

Patients will receive DPd at a dose defined by the treatment plan for up to 12 cycles, unless one of the following occurs:

- Hematologic disease progression.
- Intercurrent illness that prevents further administration of treatment
- Unacceptable adverse event(s) defined as:
  - o Occurrence of an AE that is related to treatment with the study drug which, in the judgment of the investigator, compromises the patient's ability to continue study-specific procedures, or is considered to not be in the patient's best interest.
  - o Persistent AE requiring a delay of therapy for more than 4 weeks (28 days).
- Patient decides to withdraw from the study
- General or specific changes in the patient's condition render the patient unacceptable for further treatment in the judgment of the investigator
- Patient becomes pregnant
- Patient loses the ability to freely provide consent through imprisonment or involuntary incarceration for treatment of a psychiatric or physical illness
- Patient achieves complete remission (CR), and the patient and investigator feel that discontinuation of DPd is in the patient's best interests, or
- Patient achieves a level of response that qualifies him or her for another therapy, such as high dose therapy with autologous stem cell transplantation, and the patient and investigator feel that discontinuation of DPd is in the patient's best interests.

Patients will be informed that they have the right to withdraw from the study at any time for any reason, without prejudice to their medical care. At the time of withdrawal, all study procedures outlined for the End of Study visit should be completed. The

primary reason for patient's withdrawal from the study should be recorded in the source documents and CRF.

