## Facilities Enrolling

**Participants:**

Weill Cornell Medical College-NewYork Presbyterian Hospital (WCMC/NYPH), Brooklyn Methodist Hospital (BMH), and NewYork-Presbyterian Queens (NYPQ)

Participant Duration:	Time it will take for each individual participant to complete all participant visits in the induction phase is 8 months. Patients who complete all 32 cycles of treatment for the entire study, if have not progressed or started new treatment, will be followed with disease evaluations every 90 days (+/- 30 days) until confirmed disease progression or for total duration of 24 months from last EOT visit, whichever comes first, and for survival for up to 10 years from date of enrollment or until death.
Study Agent/Device Name	
Intervention Description:	
Induction Phase (Cycles 1-8, q28 day cycles):
 
 
• Daratumumab 1800 mg SC weekly x 8 wks, 1800 mg SC q2wk days 1 and 15 (cycles 3-6) 1800 mg SC q4wk day 1 (cycles 7-8)
 
• Clarithromycin 500mg PO bid continuous until VGPR or 8 cycles, whichever occurs first
 
• Pomalidomide 4 mg PO days 1-21
 
• Dexamethasone 20 mg IV as premed days 1 and 8 (cycle 1); 20 mg PO days 2 and 9 (cycle 1); 40 mg PO as premed days 15 and 22 (cycle 1); 40 mg PO qwk (cycles 2-6); 20 mg PO qwk (cycles 7-8)
 
 
Maintenance Phase (Cycle 9+): up to 24 months q28 day cycles
 
 
• Daratumumab 1800 mg SC day 1
 
• Pomalidomide 4 mg PO days 1-21
 
• Dexamethasone 20 mg PO qwk
 

Primary Objective:	PRIMARY: To determine best response rate within 8 cycles of induction therapy.
Secondary Objectives:	SECONDARY: To determine median PFS and OS, time to response (TTR), time to progression (TTP), response duration, time to next therapy (TTNT), time to $\geq$ VGPR, ORR, CR or better rate, MRD negativity rate after 8 and 32 months, AEs in induction and maintenance phases, clinical response in high-risk groups.
Exploratory Objectives:	Assessment of MRD by multiparameter flow cytometry (MFC), FISH, NGS, PET/MRI imaging studies at best response. MFC-based tests of BM aspirates of both CD138-isolated clonal plasma cells and immune cells from marrow and tissue will be studied for various immune-based and daratumumab-based markers; dose-intensity analyses (mean relative dose intensity of dexamethasone); QoL assessments.
Endpoints:	Primary Endpoint:

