### SCHEDULE OF STUDY PROCEDURES

Screening Phase  Day-28 to 0		Treatment	End of Treatm	Post-Treatment Observation Phase
		(Cycle is 28 days) +/- 3 days for Cycle 1 and 2, +/- 7 days for Cycles 3-30	At 1 year (+/- 7 days) & 90 days after last dose of study drug (+/-7 days)	Each cycle is 90 days, +/- 30 days for 24 months or until progression
Informed consent a	X			
Inclusion/exclusion criteria review	X			
Demography/Medical history	X			
Physical Exam	X	X b (every cycle)	X	
Vital signs c	X	X d (every cycle)	X	
Weight	X	X (every cycle)	X	
ECOG status	X	X (every cycle)	X	
ECG	X			
Echocardiogram	X		X	
Pulmonary function testing e	X e		X e	
Chest x-ray f				
NYHA classification	X	X (cycle 1 only)	X	
Patient Diary g	X	X (every cycle)	X	
Concomitant medications	Continuous from time of ICF until 30 days of last treatment			
Adverse events	Continuous from time of ICF until 30 days of last treatment			
Study Drug Administration				
Daratumumab 1800 mg SC dosing h		Daratumumab 1800 mg SC on Days 1, 8, 15, and 22 of Cycles 1 and 2 (weekly dosing), on Days 1 and 15 of Cycles 3 to 6 (every 2 weeks dosing), and on Day 1 of Cycle 7 and subsequent cycles (every 4 weeks dosing)		

Clarithromycin		500 mg PO bid continuous days 1-28 of cycles 1-8 only		
Pomalidomide		Pomalidomide 4 mg PO days 1-21		

Dexamethasone		Dexamethasone (Cycle 1 D1 & 8): 20 mg IV Cycle 1 D2 & D9: 20mg PO Cycle 1 D15 & D22: 40mg PO Cycles 2- 6: 40 mg PO qwk Cycles 7- 8: 20mg PO qwk Cycle 9+: 20mg PO qwk		
Prophylactic Medications				
Varicella Zoster Prophylaxis		Valacyclovir 500mg PO qd (or equivalent, renally dosed-adjusted)		
Gastrointestinal Prophylaxis		Pantoprazole 40 mg PO daily, or other		
Laboratory Assessments				
Pregnancy test i	X	X	X	
Blood typing/indirect antiglobulin test	X			
Hematology (CBC) with differential	X	On Days 1, 8, 15, and 22 for Cycles 1 and 2; On Days 1 and 15 for Cycles 3 through 6; D1 from Cycle 7 onward and as clinically indicated	X	
Serum chemistry j	X	On Days 1, 8, 15, and 22 for Cycle 1-2, Day 1, 15 for cycles 3-6 and day 1 of each subsequent cycle	X	
Hepatitis B and C screening k	X	HBV DNA monitoring q12weeks	X	X i
Disease Assessments				
Serum $\beta$ 2-microglobulin	X			
Serum free light chains	X	X (every cycle)	X	X (every cycle)

SPEP and IFE	X	X (every cycle)	X	X (every cycle)

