#### Cycles 9-30 Maintenance (28-day cycle)

- Daratumumab 1800 mg SC q4wks on Day 1
- Pomalidomide 4 mg PO on Days 1-21 of 28-day cycle
- Dexamethasone 20 mg PO will be administered as a premedication prior to daratumumab injection on day 1 of daratumumab.
- Dexamethasone 20 mg PO weekly on non-daratumumab treatment days

During the study, assessments will be performed as shown in the Study Calendar and as clinically indicated.

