## 4.3 Duration of Study

Patients will receive D-ClaPd at a dose defined by the treatment plan for up to 30 cycles, unless one of the following occurs:

- Disease progression
- Intercurrent illness that prevents further administration of treatment
- Unacceptable adverse event(s) defined as:

Occurrence of an AE that is related to treatment with the study drug which, in the judgment of the investigator, compromises the patient's ability to continue study-specific procedures, or is considered to not be in the patient's best interest.

Persistent AE requiring a delay of therapy for more than 4 weeks (28 days).

- Patient decides to withdraw from the study
- General or specific changes in the patient's condition render the patient unacceptable for further treatment in the judgment of the investigator
- Patient becomes pregnant
- Patient loses the ability to freely provide consent through imprisonment or involuntary incarceration for treatment of a psychiatric or physical illness
- Patient achieves complete remission (CR), and the patient and investigator feel that discontinuation is in the patient's best interests, or
- Patient achieves a level of response that qualifies him or her for another therapy, such as high dose therapy with autologous stem cell transplantation, and the patient and investigator feel that discontinuation is in the patient's best interests

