### **7.4 Post-Treatment Observation Phase**

For patients who complete all 32 cycles of treatment on study, if have not progressed or started new treatment, patients will be followed with disease evaluations every 90 days (+/- 30 days) until confirmed disease progression or for total duration of 24 months from last EOT visit, whichever comes first, and for OS for up to 10 years from date of enrollment or until death.

Patients who discontinue study treatment before disease progression has been observed, will undergo disease evaluations every 90 days (+/- 30 days) as specified in the Post-Treatment Observation Phase in the Study Calendar for a duration of 24 months or until confirmed hematologic disease progression, whichever comes first.

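### The treatment cap is 12, 30 or 32 cycles depending on the section, survival contact after progression is not stated, and the age-70 premedication dose needs an explicit exception

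*Combined protocol and SAP*

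**What the plan says.** **Treatment cap**
- Section 6.11: "Patients will receive DPd at a dose defined by the treatment plan for up to 12 cycles". The regimen is named DPd, not D-ClaPd. The rows of Table 6-1 also end at cycle 12.
- Section 4.3: "Patients will receive D-ClaPd at a dose defined by the treatment plan for up to 30 cycles".
- Section 4.1, maintenance heading: "Cycles 9-30 Maintenance (28-day cycle".
- Schedule of Study Procedures, treatment column: "7 days for Cycles 3-30".
- Protocol Summary, participant duration: "Patients who complete all 32 cycles of treatment for the entire study".
- Section 7.4: "For patients who complete all 32 cycles of treatment on study".
- The summary and section 4.1 allow maintenance for at most 24 months. The summary's secondary objectives place MRD negativity at 8 and 32 months.

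**Survival follow-up**
- The 10-year period appears only in the two sentences about 32-cycle completers who have neither progressed nor started new treatment. Section 7.4 ends its sentence "and for OS for up to 10 years from date of enrollment or until death".
- For others, sections 4.3 and 7.4 say: "Patients who discontinue study treatment before disease progression has been observed, will undergo disease evaluations every 90 days (+/- 30 days", for 24 months or until progression. Section 7.5 gives the same to patients who leave for transplant.
- Section 4.3 also gives all patients 90 days of follow-up after the last dose, ending sooner if the next line starts.
- Section 8.1.6 censors OS at the last date the patient was known alive.

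**Dexamethasone premedication at age 70 or older**
- Sections 4.1 and 6.2.4 give 10 mg IV before the injections on cycle 1 days 1 and 8, and 10 mg weekly in cycles 7+. The rule is headed as applying in induction.
- Section 6.2.1.2 lists 20 mg for all patients before every injection.
- The note to Table 6-4 keeps the 20 mg premedication in place whatever dexamethasone reduction has been made.

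**The concern.** These are stopping, follow-up and dosing rules that site staff carry out, and the summary lists three enrolling facilities.

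Someone who consults 6.11 to decide when therapy ends finds a cap far below the one in 4.3. Followed literally, it would end maintenance early in responders and shorten the window for the secondary endpoint of response improvement during maintenance.

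If survival contact lapses after progression, OS is censored just when the risk of death rises. Kaplan-Meier assumes that censored patients have the same prognosis as those still followed. Here they would have a worse one, and the curve would tend to overstate survival.

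For patients aged 70 or older, two sites could give different doses before the same injection. The planned dose, which is the denominator of the exploratory dexamethasone dose intensity, would also be ambiguous.

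**Working it through.** **1. The primary design is untouched.** Section 8.1.1 gives N = 40, success at 8 or more, p0 = 9% and p1 = 25%. Exact binomial: P(X ≥ 8 | 40, 0.09) = 0.0242 and P(X ≥ 8 | 40, 0.25) = 0.818. Both meet the stated limits of 5% and 80%. The endpoint is best response within 8 cycles, and every candidate cap exceeds 8.

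**2. Cap in cycles and time.** Inputs: 28-day cycles, 8 induction cycles, month = 365.25/12 = 30.44 days. Maintenance cycles = cap − 8.

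| Cap | Days | Months | Maintenance cycles | Maintenance months |
|---|---|---|---|---|
| 12 | 336 | 11.0 | 4 | 3.7 |
| 30 | 840 | 27.6 | 22 | 20.2 |
| 32 | 896 | 29.4 | 24 | 22.1 |

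Reading 6.11 as 12 maintenance cycles after induction gives 8 + 12 = 20, which matches neither 30 nor 32. A literal 24 calendar months is 24 × 30.44/28 = 26.1 cycles, or 34.1 in total, which matches nothing. But the summary counts the 8 induction cycles as 8 months. On that convention 8 + 24 = 32, which agrees with MRD at 8 and 32 months. The 24 months is a ceiling, so 30 is not excluded.

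**3. Patients a cap could reach.** Assume exponential PFS and no other discontinuation: 40 × 0.5^(t/median). The medians are those cited in section 1.1: 4.0 and 4.2 (Pd), 7.7 (ClaPd) and 8.8 (DPd, in daratumumab-naive patients).

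| Progression-free at | 4.0 | 4.2 | 7.7 | 8.8 |
|---|---|---|---|---|
| 12 cycles | 5.9 | 6.5 | 14.8 | 16.8 |
| 30 cycles | 0.3 | 0.4 | 3.3 | 4.5 |
| 32 cycles | 0.2 | 0.3 | 2.8 | 3.9 |

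The 12-cycle row is an upper limit for patients still in maintenance, because maintenance requires PR or better and some progression-free patients will have less.

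**4. Survival contact by group.**

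| Group | Disease evaluations after treatment | Survival contact stated |
|---|---|---|
| Completes 32 cycles, no progression or new therapy | Every 90 days, up to 24 months | Up to 10 years from enrollment |
| Stops before progression | Every 90 days, up to 24 months or progression | None as such, but each visit updates the last-known-alive date |
| Progresses on treatment | None | None after 90 days, or after the next line starts if sooner |

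On the assumptions of step 3, about 0 to 4 of 40 fall in the first row. The documents do not give the split of the rest between the second and third rows.

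For a patient who stops at progression at the median PFS, the last stated contact is at most median + 90/30.44 = median + 3.0 months. Paired with the median OS cited from the same study:
- Pd phase 3: 4.0 + 3.0 = 7.0, against 12.7 months.
- Pd phase 2: 4.2 + 3.0 = 7.2, against 16.5 months.
- ClaPd: 7.7 + 3.0 = 10.7, against 19.3 months.
- DPd: 8.8 + 3.0 = 11.8; no OS median is cited.

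**5. Premedication at age 70 or older.** Induction injections: 2×4 + 4×2 + 2×1 = 18. The age rule gives 20 mg on 14 of them, where there is no conflict. It gives 10 mg on 4: C1D1, C1D8, C7D1 and C8D1.
- Planned induction dexamethasone under the age rule: 4×20 + 5×4×20 + 2×4×10 = 80 + 400 + 80 = 560 mg.
- With 20 mg on the 4 conflicting days: 560 + 4×10 = 600 mg (+7.1%). Week 1 is 20 or 30 mg.
- Each maintenance cycle is 4×10 = 40 mg if cycles 7+ includes maintenance, 20 + 3×10 = 50 mg if the 20 mg rule also holds on day 1, and 4×20 = 80 mg if the age reduction ends with induction.

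**The case against.** **Cap.** The 12 is outnumbered by every other statement of treatment length and carries another regimen's name, so few sites would follow it. The text below Table 6-1 covers dose delays from cycle 7 onwards, which largely repairs the short table. A reader might infer that responders will in fact be taken off therapy at cycle 12. The documents do not support that as the intention. What stands is that the sentence is current text in the termination section, and that removing it still leaves 30 against 32.

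**Survival.** A reader might infer that almost nobody has survival contact beyond 90 days, or nobody at all if the cap is 12 or 30. That goes too far. Everyone who stops before progression, including transplant patients, has visits every 90 days for up to 24 months, and each visit moves the OS censoring date. Progression-free patients reaching a cap of 12 or 30 would most naturally fall under the same rule. Section 7.3 gives the purpose of the 90 days as detecting late toxicity, so it does not prohibit later contact. The 10-year clause may also be a study-wide rule attached to a badly built sentence. What stands is that no section states survival contact for patients who progress.

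**Premedication.** The age rule names its doses and days, so it can be read as a specific exception. The Table 6-4 note is written for dose reductions. The 20 mg in 6.2.1.2 is generic: younger patients take 40 mg before several injections. The exception reading is plausible, but neither 20 mg rule says so, and the induction heading leaves cycles 7+ unclear.

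**Conclusion.** The point holds as three inconsistencies in current operative text that should be fixed.

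- **Cap:** three values, giving 4, 22 or 24 maintenance cycles. The best-supported value is 32, counting a cycle as a month as the summary does. Between 30 and 32 the difference is two cycles for at most about 5 of 40 patients, on exponential PFS with the cited medians.
- **OS:** the gap is survival contact after progression, plus the missing long-term wording for patients who stop early. Where PFS and OS come from the same cited study, the last stated contact for a patient progressing at the median falls 5.7 to 9.3 months before median OS (12.7 − 7.0; 16.5 − 7.2). This is illustrative. It shows a risk of informative censoring, not a measured bias, and records may capture deaths anyway.
- **Premedication:** 4 of 18 induction injections and 40 mg (+7.1%) over induction, and possibly day 1 of every maintenance cycle. The number of patients aged 70 or older is not given. The analysis affected is exploratory.

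A reader might infer that the trial's main conclusion is at risk. It is not: the 8-cycle primary endpoint and the 8-of-40 rule do not depend on any of these texts.

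**What to change.** 1. **Cap.** Put one number in 4.1, 4.3, 6.11, 7.4, the summary and the schedule of procedures: 32 if 8 induction plus 24 maintenance cycles is meant; otherwise change the 32s to 30. Name the regimen D-ClaPd in 6.11, and extend the last row of Table 6-1 to the end of treatment.
2. **OS.** State in the summary and 7.4 that survival follow-up for up to 10 years from enrollment applies to all enrolled patients, whatever the reason for stopping, by chart review or telephone.
3. **Age 70 or older.** Add the age rule as an explicit exception in 6.2.1.2 and in the Table 6-4 note. State whether cycles 7+ includes maintenance, and use the resulting schedule as the dose-intensity denominator. Giving 20 mg on injection days and dropping the day 2 and 9 doses would also remove the conflict in cycle 1, but that is a clinical trade-off, not a wording correction.

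The cost is a consistency amendment and a site memo, with no added patients or clinic procedures. The small downside is longer survival contact for more patients.
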